#### 2.2 Background

Post-stroke aphasia is a prevalent neurological disability with a negative impact on quality of life. Aphasia is a neurological deficit defined by the impaired ability to process language as a result of brain damage. It is one of the most common forms of neurological disabilities after a stroke, typically resulting from injury affecting the language-dominant brain hemisphere. At least 20% of all stroke survivors remain with some degree of long-lasting aphasia. Since language is one of the most essential components of human interaction, aphasia has a profound and negative impact on quality of life. Post-stroke aphasia often leads to social isolation, worse rehabilitation outcomes, and depression.

#### 2.2.1 Non-fluent aphasia

Individuals with aphasia can exhibit different types of language impairments, and aphasia is classified in accordance with the patterns of linguistic difficulties exhibited by each person. Non-fluent aphasia is defined by significantly reduced speech production, ranging from total mutism to utterances composed of only 3-5 words. Non-fluent aphasia is not only a very common type of aphasia, affecting approximately 40% of all chronic aphasia cases, but also one of the most debilitating types. Non-fluent aphasia is frequently associated with profound frustration and depression.

Slow speech, effortful speech, frequent pauses, short phrase length, single words, and poor articulation are commonly observed in subjects with non-fluent aphasia. There is not a perfect diagnostic tool for non-fluent aphasia, given the complexity of the symptoms that may lead to fluency problems. Nonetheless, one of the most robust tools for this purpose is the Western Aphasia Battery, revised edition (WAB-R), which, in spite of being relatively general, permits a reproducible agreement across clinicians and researchers. The WAB-R is one of the most commonly used tools in daily practice and basing this current research on the WAB-R will permit a clinical translation in the future[see section 1.4].

This research will focus on the recovery of spontaneous speech and will include all forms of non-fluent aphasia, except for global aphasia. Global aphasia is a very severe form of aphasia, with suboptimal recovery potential and, unfortunately, is rarely associated with improvement in fluency.

#### 2.2.2 Speech Entrainment Therapy (SET)

The basic premise behind most rehabilitation approaches, regardless of the targeted function or modality, is that repeated practice of a specific behavior within the therapy session leads to an increased likelihood that this behavior improves and can be executed outside the rehabilitation setting. This concept is related to the principle of Hebbian learning, which is based on the notion that synaptic strength and functional neuronal connections can be reinforced due to repeated stimulation and new experiences lead to molecular and cellular events that alter synaptic efficacy, leading to reorganization of neuronal circuits. This principle should be considered in the context of aphasia therapy since conventional therapies typically induce numerous speech errors. In fact, treatment-induced errors can often exceed correct responses. Based on the Hebbian learning principles of neuroplasticity, it is possible that repeated errors could, in fact, lead to maladaptive changes and contribute to the persistence of post-therapy errors and non-fluent speech. In contrast with conventional speech therapies, SET enables subjects with aphasia to practice fluent speech with few errors, which is, otherwise, unachievable. This innovative and unique feature of SET differentiates it from other forms of speech therapy. We know of no other method, besides SET, that enables non-fluent aphasic subjects to produce fluent, prosodically accurate, speech for a prolonged period of time.

#### 2.2.3 Overcoming learned nonuse

SET also directly addresses the issue of 'learned nonuse,' which implies that stroke survivors tend to avoid using affected functions because doing so is inefficient, relying instead on the spared functions. In the context of motor impairments, learned non-use is manifested by the preferential use of the spared limb, with little or no use of the paretic limb. Although learned nonuse has not been frequently addressed in the aphasia literature, it is clear that non-fluent subjects tend to withdraw from communication situations. SET provides non-fluent stroke subjects with the opportunity to practice fluent speech and reverse some of the effects of learned nonuse in speech.

#### 2.2.4 Theoretical framework and mechanism of action of SET

There is abundant evidence from the current neuroscience literature to suggest that the adult brain is capable of reorganization after injury. Cortical representation, maps, and networks can be modified by new experiences and learning. Nonetheless, reorganization is less likely to occur in brains with larger injuries or in older age.

The mechanism of action of SET is the sensorimotor transformation of speech, enabling the reproduction of the speech that is heard and seen. It entails the online transformation of auditory and visual signals into articulation and phonological output. As such, SET overcomes (or compensates for) speech production deficits but requires that auditory comprehension to be at least partly intact.

Overall, SET-mediated improvements are likely related to the involvement of brain areas responsible for sensorimotor transformation of speech. Our preliminary data indicate that subjects who benefit the most from SET are those with preserved sensorimotor speech brain areas located in the temporal-parietal junction, which is a hub for sensorimotor transformations for vision, movement, and language. Within the left temporal-parietal region, area Spt (left posterior Sylvian region at the parietal-temporal boundary) is specialized in language sensorimotor integrations. It plays a similar role in speech compared with other well-known areas responsible for sensorimotor integration of other modalities, such as the lateral intraparietal cortex (area LIP) for eye movement in primates, and the anterior intraparietal cortex (area AIP) for upper extremity reach and grasp. SET-related improvements likely depend on the functional and structural integrity of area Spt prior to therapy.

Nonetheless, SET-mediated recovery may be related to different brain regions depending on the aphasia type. More specifically, for subjects with intact repetition (transcortical aphasia), SET improvement may be related to recruitment of more anterior regions (frontal associative areas).

It remains undefined for whom, why, and how much SET can be of benefit. It is very likely that, within the category of non-fluent aphasia, individuals with different aphasia types (and, thus, with different levels of repetition and comprehension impairment) may benefit differently. For this reason, this study will focus on evaluating whether SET is indeed associated with consistent results, and whether the improvement achieved with SET is comparable with an effect size reported in the literature for conventional speech therapy. If SET is indeed determined to be associated with therapeutic benefits, a "go" decision will be made for a future definitive clinical trial comparing SET with other forms of therapy. During this future study, it will be paramount to determine the individual determinants of therapy success, not only to better inform clinicians, but also to evaluate the mechanisms associated with differential responses from SET versus other forms of therapy.

#### 2.2.5 Evidence-based speech therapy for non-fluent aphasia

One of the most important challenges in establishing evidence-based aphasia treatment is related to the fact that most of the existing literature is based on "small numbers of participants across a range of characteristics (age, time since stroke, and severity profiles), interventions, and outcomes" as described by the 2012 and 2016 Cochrane Reviews. This study aims to directly overcome this challenge by performing a controlled trial with a large number of subjects targeting a specific yet common form of aphasia (non-fluent aphasia).

Although there is evidence suggesting that behavioral treatments for non-fluent aphasia can lead to improvements in spontaneous speech, it is relatively uncommon for subjects with non-fluent aphasia to recover to a point where their speech could be considered fluent with the existing therapies, particularly in the chronic phases after the stroke.

At the moment, there is no completely satisfactory approach for treating spontaneous speech production in non-fluent aphasia, which constitutes an important and unmet clinical gap

in the neurorehabilitation of stroke. This is a well-recognized area for improvement and past and current clinical trials have attempted to assess new approaches to treat aphasia, including Constrained-Induced Aphasia Therapy (CIAT) (ClinicalTrials.gov Identifier NCT00843427), Melodic Intonation Therapy (NCT00903266), transcranial direct current stimulation (tDCS) (NCT01686373), tDCS coupled with Dextroamphetamine (NCT02514044) and transcranial magnetic stimulation (TMS) (NCT00608582, NCT02241213, NCT01512264).

While these are promising new avenues of treatment, we believe that the therapy being proposed in the current trial, speech entrainment therapy (SET), is unique and, perhaps, superior to other forms of therapy because it enables subjects with aphasia to practice

relatively error-free, fluent speech. SET guides the reestablishment of speech fluency, thus overcoming the initial barrier between non-fluent to fluent speech, which is not often observed with other therapies.

Moreover, SET may circumvent speech errors that are commonly associated with conventional speech therapies. To the best of our knowledge, the only other form of therapy that induces relatively error-free speech is Melodic Intonation Therapy (MIT). However, MIT propitiates practice in verbal output with a prosody that is different from actual speech and, therefore, is less ecologically realistic. For this reason, SET may be a better approach to permit practice in fluent speech. The significance and innovation of SET are further explained in detail below.

#### 2.2.6 Significance of SET

In a preliminary study, we reported

Pre SET 3 Months Post SET

Average 3 months post - pre treatment VPM=1.11 (SD=1.98)
Group mean improvement in VPM=22.2%

T=2.2 p=0.047
Standardized effect size=0.56

Figure 2. Preliminary data - SET delivered once a day, 5 times a week for three weeks was associated with significant gains in spontaneous speech production, which were sustained at 3 months after the conclusion of SET. The box-plot demonstrates the VPM data before and after SET (with the vertical histograms on the right side to further illustrate the distributions of the data points in the box-plots).

SET as a new form of speech therapy to enable individuals with non-fluent aphasia to produce fluent speech. During the SET session, the participant's speech is "pulled along" (guided) by an audiovisual (A/V) model in which the therapist's mouth is seen on a computer screen and the speech is heard via headphones (for an illustrational video, please refer to https://youtu.be/rseSnWq9C\_U).

It is important to point out that speech repetition ability and speech entrainment ability dissociate in most participants with non-fluent aphasia. That is, many participants with very poor repetition (as in the case of most non-fluent participants) can still produce fluent speech with speech entrainment. However, it is not known whether SET success depends on the degree of speech repetition impairment, or the degree of auditory comprehension deficits. Our preliminary data provided the "proof of concept" to justify a phase II clinical trial to achieve a detailed assessment of SET effect size and estimate type of linguistic improvements and response variability.

#### 2.2.7 Preliminary study and pilot data for Specific Aim 1

Our supporting data are based on two studies: the first one (preliminary published study, described in more detail below) was published by our group in 2012 in the journal *Brain*, and the goal of that study was to determine the feasibility of SET as a clinical approach to treat non-fluent aphasia. That initial study focused on comparing delivery modes of SET and used speech metrics, such as the number of words per minute, and speech fluency ratings from the WAB-R. Subsequently, we determined that, while these measures may be adequate to assess aspects of discourse, they are possibly not the most sensitive measures of the effects of SET, and not the most reliable representations of speech abilities (e.g., a participant may repeat a noun several times but not improve communication). For this reason, we conducted a separate study (pilot data also described in more detail below), which was directly intended to provide preliminary data for this application. This second study used a similar dose of therapy as the current trial (3 weeks) and measured its effects on the same primary endpoint proposed here (VPM).

#### 2.2.8 Preliminary published study

Fridriksson et al. (2012) was a preliminary study by our group, which provided the initial proof of principle for the effectiveness of SET. This study detailed: 1) the creation and implementation of SET using an A/V feedback system; 2) that SET using an A/V model is better than SET using an audio model alone; and 3) the effects of SET on speech production among 13 subjects with chronic non-fluent aphasia after 6 weeks of daily therapy. During SET, the subject used a laptop to view a video of the therapist's face (below the nose), listened to the audio via headphones, and mimicked the speech in real time. The topics were: the weather in the United States, how to make scrambled eggs, or describing the Thanksgiving holiday. Each subject underwent language testing 1 week before and 1 and 6 weeks after therapy. During SET, the subjects' speech was more fluent than their speech outside of therapy. The subjects who underwent SET produced statistically significantly more words during discourse 1 week after treatment (p<0.05). They were also nearly better at producing more VPM at 6 weeks after treatment (p=0.06), but this effect was limited due to the reduced power from a small sample size.

In Fridriksson et al. (2012), we observed that subjects with aphasia experienced an improvement in overall speech fluency associated with SET (standard deviation=1.7%, t= 2.76, p=0.009). Speech fluency was assessed by tallying the number of different words and recording the percent of correctly produced words per script. In addition, SET was associated with an increase in ratings of information content.

#### 2.2.9 Telehealth as a mode of service delivery

All visits will be performed via telehealth, with the exception of the optional MRI at study completion. The use of telehealth as a successful service delivery mode has been studied in the field of Speech Language Pathology for use with post-stroke aphasia. A study by Woolf et al. (2016) compared the effects of Aphasia Remote Therapy (ART), In-Clinic Therapy (I-CT), and attention therapy in a group of individuals with chronic aphasia and found no difference between ART and I-CT. A group study (N=44; 37 had aphasia) conducted by Meltzer et al. (2018) compared I-CT to a hybrid version of ART with one session a week of clinician administered therapy via telerehab, which was heavily supplemented with computerized

homework at least four times a week. This study found hybrid ART to be non-inferior to I-CT. The American Speech-Language Hearing Association (ASHA) also has set up guidelines for telepractice in Speech-Language Pathology.

Because SET is already an audiovisual computer program, telehealth will be compatible as a mode of service delivery. Our team has many experienced SLPs specializing in treatment of aphasia and, to our advantage, are already trained in the use of telehealth in aphasia research due to participation in an ongoing study that utilizes telehealth (C-STAR POLAR). This team developed an ART application that has been successfully utilized in POLAR, and this same team has developed an application specific for this trial. Technology support staff will provide on-call technology support for all sites during the trial.

#### 2.2.10 Significance of the knowledge to be gained

Our pilot data suggest that SET can be a groundbreaking, innovative, and clinically feasible approach to treat aphasia. This study will provide a complete and controlled evaluation of SET and provide the important triage before costly head-to-head studies with other forms of speech therapy.

#### 2.3 Risk/Benefit Assessment

#### 2.3.1 Known Potential Risks

For the current research, three areas are of paramount interest with regard to the protection of human subjects: 1) Potential adverse effects associated with MRI scanning; 2) Potential adverse effects associated with behavioral testing and treatment; and 3) Maintenance of participant confidentiality. We will address each of these below on a point-by-point basis.

#### 2.3.2 MRI Scanning

All participants have the option to participate in an MRI once they have completed treatment. We find that most participants who have reported negative reaction to past MRI experiences do not have problems with our MRI setup. The MRI scanners used for this research are short-bore magnets (Siemens 3T Trio) with a wider bore than most older generation scanners. This allows the participant rather easily to see through either end of the scanner bore without shifting head position.

All participants will undergo thorough screening to check for factors counter-indicative for MRI scanning. The optional MRI scanning will not be conducted in participants with contradications. We will follow the same protocol that we have used with past participants. First, each person fills out a questionnaire in collaboration with a clinician and, when needed, a caregiver. Then, we give each participant ample time to get familiar with the scanner before the actual scanning session starts. We find that when taking this extra time to familiarize participants and, when appropriate, family members, with the MRI setup, participants usually feel comfortable with the MRI session.

#### 2.3.3 Participant Testing & Treatment

In our experience, occasional participants will have a negative reaction to neuropsychological testing. For example, this can be caused when participants realize that their performance on a given test is far worse than they would have expected. We always make sure that ample time is allotted for neuropsychological testing and that participants are allowed

breaks as needed. With regard to the behavioral treatment, the only adverse reaction that we occasionally see is fatigue. This is something that we warn participants about ahead of time.

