Assessment	Screening &	Baseline	nent recording ar Intervention	Follow-Up	Follow-Up	Follow-Up
	Randomization Visit 0 Days -5 to 0	Assessments Visit 1 Days 1-5 (+/-4 days)	Period Visits 2-30 a For 3, 4.5, or 6 weeks (+/- 3 days)	Visit 1 1-week post intervention b (+/- 3 days) c	Visit 2 3-month post intervention b (+/- 1 week) c	Visit 3 6-month post intervention b (+/- 1 week) c
Informed consent	Χ					
Review of eligibility criteria and randomization	Х					
Concomitant Aphasia Treatment				X		Х
Assess New Adverse Events			X	Χ		
Verbs per Minute (VPM)		Χ		Χ	X	X
Gathering of individual demographic and baseline characteristics (Table 3)		X				
NIH Stroke Scale (NIHSS)	X					
Western Aphasia Battery- Revised (WAB-R)	X d, e			Х	Х	Х
Quality of life assessment - Stroke and Aphasia Quality of Life (SAQOL-39g)		Х		X	X	X
Charlson Comorbidity Index		Χ				
Communicative Effectiveness Index (CETI)		X		X	X	
Lexical Orthography Familiarity Test (LOFT)		Х				
Modified Epworth Sleepiness Scale (ESS)						
Apraxia of Speech Rating Scale 3.0 (ASRS 3.0)	X d			X	Х	
Pyramids and Palm Trees Test (PPTT)		Х				
Matrix Reasoning - Wechsler Adult Intelligence Scale, Third Edition (WAIS-III)		Х				
Vertical Numerical Rating Scale-Face Rating Scale for post-stroke fatigue (NRS- FRS)		Х				
Modified Philadelphia Repetition Test (PRT)		X		X	Х	
Modified Philadelphia Naming Test (PNT)		X		X	Х	
Stroke Aphasic Depression Questionnaire (SADQ-10)		X				
MRI					(opt	ional)

Footnote: aNumber of visits depend on randomized arm. bFollow-up assessments can be completed over 1-5 days. cDefinitions for the follow-up visit target date and window provided in Table 2. dRepeat WAB-R/ASRS 3.0 measures prior to intervention if initiation of intervention period occurs >15 days post randomization. eUse of WAB-R scores obtained for other purposes, administered within 120-days before randomization, is allowed.

Note: In the event of technological difficulties, readministration of baseline or follow-up testing will be conducted within study timeline constraints to maintain the integrity of data collection.

Table 2. Follow-Up Visit Target and Visit Windows in Days						
Randomization	Follow-Up	Follow-Up	Follow Up			
Assignment	Visit 1	Visit 2	Visit 3			

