# 1.3.3.1 Assessment of Adverse Events

We will ask the participant to report adverse events (AEs) as they occur and will routinely ask the participant at the end of each week of intervention. We will also call each participant in the no SET group weekly to assess AEs. See section 8.2 for more information regarding the definition and classification of AE and guidelines for reporting events.

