# 3.0 Objectives and Endpoints

Objectives	Endpoint	Justification			
Primary					
To estimate the dose of SET for individuals with non-fluent aphasia that has the highest effect size on VPM.	Verbs per minute (VPM) at 3 months post-treatment/control period.	*See justification below			
Secondary					
To estimate the dose of SET for individuals with non-fluent aphasia that has the highest effect size on SAQOL-39g.	SAQOL-39g at 3 months post- treatment/control period	To assess if improvements in fluency from SET are related to gains in quality of life.			
Safety and Tolerability	Safety and Tolerability				
To assess the tolerability and safety of SET	Number of treatment sessions completed	Adequate tolerability would be completion of at least 80% of the treatment sessions.			

Exploratory	Adverse Events possibly/probably/definitely related to study treatment and Serious Adverse Events	Although this study intervention is low-risk, there is the potential for risk in any clinical trial.
To estimate the dose of SET for individuals with non-fluent aphasia that has the highest effect size on the WAB-R, CETI, and ASRS 3.0.	Scores at 3 months post-treatment/control period.	To assess if improvements in fluency from SET are related to gains in other speech and/or quality of life measures.
To estimate the effect of SET on VPM, WAB-R, SAQOL-39g at early and late time points.	1-week post and 6 months post	The primary time point of interest is the 3 months post, but the 1 week and 6 month post assessments will be explored to assess whether benefits are sustained over time

\*The primary endpoint for this trial is VPM at three months post-conclusion of SET or control. VPM is a measurable representation of spontaneous speech production. This primary endpoint was chosen for the following reasons:

- 1) Spontaneous speech is an important "real-life" aspect of language. It has a direct effect on conversation and social aspects of language, and directly informs on practical and meaningful elements of communication.
- 2) The use of verbs during spontaneous speech provides a reliable measure of language abilities and effectiveness of communication.
- 3) It is not surprising that many individuals with aphasia can achieve improved fluency during the SET session. However, for SET to have a clinical impact, it should lead to sustained benefits that remain after the therapy. Benefits that can last at least 3 months after therapy are highly important.

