#### 9.4.6 Safety Analyses

Monitoring Plan for Worsening in the Primary Outcome: If SET leads to substantially worse outcome than the no SET arm, early stopping may be considered. The unblinded statistician will fit the primary analysis model semi-annually in order to compare VPM between the combined SET durations versus No SET (one-sided  $\alpha$ =0.025). As part of this analysis, outliers will be explored to ensure that the results are not driven by a specific individual. Should the null hypothesis be rejected, an investigation of dose response among the SET arms based on qualitative evaluation (i.e. not statistical) when ordered in terms of dose level will occur. Should a dose response relationship be detected, the unblinded statistician will bring this to the attention of the DSMB and investigators.

All AEs and SAEs are summarized by preferred term according to the Medical Dictionary for Regulatory Activities (MedDRA) adverse reaction dictionary in terms of frequency of the event, number of subjects having the event. For the Closed DSMB report, severity, and relatedness to the treatment will also be shown by treatment group.

At the end of the trial, the cumulative incidences of the specific SAEs related to treatment, as well as all SAEs, will be compared across groups.

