### **Safety Monitoring**

The unblinded statistician at the DCU will produce semi-annual DSMB reports and at the request of the DSMB. The Closed Session DSMB reports will show tables by partially blinded treatment group. All serious adverse events will be summarized by “preferred term” and associated system-organ class according to the MedDRA dictionary and by treatment group in terms of frequency of the event and number of subjects having the event. For the DSMB report, severity and relatedness to the study drug will also be shown by treatment group.

At the end of the trial, the cumulative incidences of the specific SAEs related to treatment, as well as all SAEs, will be compared across groups.

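### SAP Section 12 tabulates only serious adverse events, so the related non-serious events in the protocol's safety endpoint, fatigue among them, have no planned SAP table

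*Protocol*

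**What the plan says.** Protocol 2.3.3 states that, with the behavioral treatment, "the only adverse reaction that we occasionally see is fatigue". Protocol 3.0 gives two safety and tolerability measures: sessions completed, and "Adverse Events possibly/probably/definitely related to study treatment and Serious Adverse Events".

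On collection, Protocol 1.3.3.1 says that staff "will routinely ask the participant at the end of each week of intervention", and for the control arm: "We will also call each participant in the no SET group weekly to assess AEs". Table 1 also marks the AE assessment at Follow-Up Visit 1. Under Protocol 8.2.3 a non-serious AE always goes in the chart, but it is reported onward only when the site principal investigator (PI) judges it related to the intervention. SAEs are always reported.

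On analysis, Protocol 9.4.6 says: "All AEs and SAEs are summarized by preferred term". It adds severity and relatedness by treatment group for the Closed DSMB report. The Safety Monitoring part of SAP 12 applies the same preferred-term tabulation by treatment group to serious adverse events alone. Both documents then close with the same sentence on the end of the trial: "the cumulative incidences of the specific SAEs related to treatment, as well as all SAEs, will be compared across groups".

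Table 1 schedules the "Vertical Numerical Rating Scale-Face Rating Scale for post-stroke fatigue" at baseline only, and Table 3 lists post-stroke fatigue as a baseline characteristic.

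**The concern.** The SAP is the document that the analyst programs from, and on this point it is narrower than the protocol. The protocol's endpoint has two parts, related AEs and SAEs. The SAP names an analysis for SAEs only. The one reaction that the protocol expects from the treatment belongs almost entirely to the part that the SAP leaves out.

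The trial exists to choose among 15, 22 and 30 hourly sessions. Its safety results should at least show, arm by arm, how often the expected reaction was reported. If the final report follows the SAP, readers would see SAE counts, in which treatment fatigue would rarely appear, and no table of related non-serious events, although these are a stated endpoint and are collected.

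**Working it through.** The documents give no figure to reproduce here, so the check sets the passages side by side.

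**1. Which events each passage covers**

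| Place | Related non-serious AEs | SAEs |
|---|---|---|
| Protocol 3.0, safety endpoint | yes | yes |
| Protocol 8.2.3, reporting | yes, if the site PI judges them related | yes |
| Protocol 9.4.6, summary by preferred term | yes | yes |
| Protocol 9.4.6, end-of-trial comparison | no | yes |
| SAP 12, summary by preferred term | no | yes |
| SAP 12, end-of-trial comparison | no | yes |
| Any other SAP section | none named | none named |

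The SAP's general approach (Section 2) promises descriptive statistics by arm but does not say that non-serious AEs are among the variables. SAP Section 10 covers session participation. The rest of SAP 12 is the monitor for worsening VPM. The SAP change log ties its Section 12 entries to that monitor, so nothing there records a decision to drop non-serious events.

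**2. Where fatigue falls.** The SAE criteria in Protocol 8.2.2 are death, threat to life, hospitalization, lasting disability, birth defect, or an event needing intervention to prevent one of these. Fatigue after an hour of speech practice would seldom meet any of them. That is a judgment; the documents give no rate.

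**3. How fatigue could still surface.** There are three routes:
- the all-AE summary in Protocol 9.4.6;
- the Closed DSMB report, with severity and relatedness by arm;
- the participation rates by arm in SAP 10. This route is blunt, because Protocol 1.3.3.2 allows make-up sessions and SAP 10 allows for sessions out of window, so a tired participant who finishes counts as complete.

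**4. Why raw counts would mislead even once tabulated.** Suppose 20 participants per arm, one AE query per treatment week, full participation, and the same probability r of a fatigue report at each query in every SET arm, so that there is no dose effect. Expected reports during treatment are:
- Arm A: 20 × 3 × r = 60r
- Arm B: 20 × 4.5 × r = 90r
- Arm C: 20 × 6 × r = 120r

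The ratio of C to A is 120r / 60r = 2, and of B to A it is 90r / 60r = 1.5, from length of observation alone. Dividing by participant-weeks (60, 90, 120) returns r in each arm.

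A window of the first 3 weeks also equalizes observation. However, all SET arms follow the same daily schedule in those weeks, so this window checks comparability and cannot show the effect of longer treatment. What is specific to duration lies in the later weeks, which is why the per-week figures are needed too.

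**5. The control arm.** Control participants are called weekly, but under Protocol 8.2.3 their non-serious events are reported only if related to an intervention that they do not receive. Their fatigue would mostly stay in the chart. Protocol 4.1.1 says that research staff and participants know the arm, and nothing says that the site PI is blinded when judging relatedness. The control arm therefore supplies no clean background rate.

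**The case against.** The strongest reply is that the data are collected and the protocol already commits to analyzing them. AEs are asked about weekly in all four arms, related ones are reported, and Protocol 9.4.6 would list fatigue by preferred term. This stands. A reader might infer that dose-related fatigue cannot appear in the safety results at all, and the documents do not support that.

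A second reply is that the SAE-only sentence in SAP 12 follows directly on the description of DSMB reports, so it may describe only what those reports contain and leave the protocol's summary in force. That is a fair reading, and it means that the part of the endpoint concerning related AEs is not shown to be lost. It does not remove the mismatch: Protocol 9.4.6 expects relatedness and severity of all AEs in the Closed DSMB report, and no SAP section takes up the wider summary.

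A third reply is that the SAE-only end-of-trial comparison is the same in both documents and so is a consistent choice. It is consistent, but it still leaves half of the wording of the Section 3.0 endpoint out of the only final cross-arm safety comparison that is named.

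Finally, the baseline-only fatigue scale might be read as an error. It is not. No document promises a fatigue outcome, the scale is presented as a baseline characteristic, the protocol calls the intervention low-risk, and the selection rule uses VPM and participation only. AE capture is a legitimate way to follow an occasional reaction.

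**Conclusion.** The point holds as a mismatch between the protocol and the SAP, with a practical consequence. Followed as written, the SAP leaves related non-serious AEs untabulated, and these include the only reaction to SET that the protocol names. It should be corrected before analysis, but it is modest in size: the primary analysis, the effect-size estimates and the choice of duration are unaffected.

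The conclusion rests on three assumptions: that treatment fatigue will rarely be serious; that the related events reported under Protocol 8.2.3 are those in the possible, probable and definite categories of Section 3.0; and that the analyst takes the SAP as the working specification. The twofold difference in observation between arms C and A further assumes one query per treatment week.

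**What to change.** **SAP 12, Safety Monitoring.** Widen the tabulation from serious adverse events to all reported AEs and SAEs, to agree with Protocol 9.4.6.

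**SAP 12 and Protocol 9.4.6, end of trial.** Add AEs possibly, probably or definitely related to treatment to the by-arm summary, with fatigue as its own row. Keep this descriptive. Give totals, and also figures per week of observation and over a common window such as the first 3 weeks.

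**Footnote to that table.** State that non-serious AEs were reported only when judged related by the site PI, in a trial whose site staff knew the arm, so the control column is not a background rate.

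The cost is wording and one or two extra table shells. No new data, visits or staff are needed.

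**Optional, and not the correction of an error.** If the sponsor wants a fatigue-by-dose estimate on a scale, the single-item 0-10 rating could be repeated at the weekly contacts already made in all arms. It adds a small burden, the control calls are by phone so the scale would have to be read aloud or shown by video, and self-report by unblinded participants against a no-treatment arm is open to bias. The documents give no variance for the scale, so its precision cannot be stated without assumption.
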